#### **5.4 Duration of Follow Up**

Patients will be followed for *minimum of 30 days, or longer* after removal from protocol treatment or until death, whichever occurs first. Patients removed from study for unacceptable adverse event(s) will be followed until resolution or stabilization of the adverse event.

## 6. DOSING DELAYS/DOSE MODIFICATIONS

### 6.1 Dosing Delays

Once a cycle is started, prescribed therapy will not be delayed. Patients unable to take veliparib due to toxicity will have those doses skipped.

For patients achieving CR, CRI, PR, or MR following cycle 1, a repeat cycle of the same regimen may be administered beginning no sooner than Day 28 of the preceding cycle and no later than Day 63 from the initiation of the previous cycle (see **Section 5.1**). Delays beyond day 63 should be reviewed with the principal investigator and may be approved if patient is deemed be achieving clinical benefit.

### 6.2 Veliparib Dose Reductions

Veliparib dose will not be adjusted due to end organ dysfunction.

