### **3.2 Randomization Eligibility Criteria**

3.2.1 Bone marrow aspirate and/or peripheral blood specimens were submitted to the central lab and site has confirmation by the local institution that the patient meets one of the criteria specified in 3.1.1 above.

3.2.2 Age  $\geq 18$  years. Because no dosing or adverse event data are currently available on the use of veliparib in combination with topotecan and carboplatin in patients  $<18$  years of age, children are excluded from this study, but will be eligible for future pediatric trials.

3.2.3 ECOG performance status  $\leq 2$  or Karnofsky  $\geq 60\%$  (see Appendix A).

3.2.4 Patients must have normal organ function as defined below:

- Total bilirubin	less than 2.0 mg/dL unless due to Gilbert's Syndrome, then less than 5.0 mg/dL
- AST(SGOT)/ALT(SGPT)	less than $5 \times$ institutional upper limit of normal
- Creatinine Clearance	GFR greater than 30 ml/min per modified Cockcroft-Gault formula

3.2.5 Interval of greater than 4 weeks since allogeneic blood or marrow transplantation (BMT) if performed; and absence of active GVHD

3.2.6 The effects of veliparib on the developing human fetus are unknown. For this reason and because PARP inhibiting agents as well as topoisomerase inhibitors and platinating agents are known to be teratogenic, women of child-bearing potential must agree to use adequate contraception (hormonal or barrier method of birth control; abstinence) prior to study entry, for the duration of study participation, and for 6 months following the last dose of study drug. Should a woman become pregnant or suspect she is pregnant while she or her partner is participating in this study, she should inform her treating physician immediately. Men treated or enrolled on this protocol must also agree to use adequate contraception prior to the study, for the duration of study participation, and 4 months after completion of veliparib administration.

3.2.7 Ability to understand and the willingness to sign a written informed consent document.

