### 6.3 Topotecan and Carboplatin Dose Reductions

Topotecan should dose-reduced for decreases in creatinine clearance (CrCl) using modified Cockcroft-Gault formula as follows:

CrCl >40 ml/min: no reduction

CrCl 20-39 ml/min: 50% reduction

CrCl <20 ml/min: topotecan will not be given

Carboplatin should be dose-reduced for decreases in CrCl as follows:

CrCl 40-59 ml/min: 30% reduction (give 70% original dose)

CrCl 16-39 ml/min: 45% reduction (give 55% original dose)

CrCl  $\leq$  15 ml/min: carboplatin will not be given.

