In human, ABT-888 (veliparib) clears primarily in the urine as intact parent drug along with metabolites suggesting that renal function plays an important role in the drug clearance and its metabolites. Drug-associated with kidney toxicities or kidney diseases could change ABT-888 (veliparib) pharmacokinetics. Use cautions when concomitantly administer oxaliplatin, carboplatin, cisplatin, and topotecan in patients with pre-existing renal impairment.

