### **Pharmacokinetics**

**Absorption:** The absorption of veliparib after oral dosing was relatively rapid, with average time to maximum observed plasma concentration (Tmax) ranging from 1 to 2 hours across dose levels. The maximum observed plasma concentration (Cmax) and the area under the plasma concentration curve from time zero to infinity (AUC $\infty$ ) of veliparib were approximately dose-proportional across the dose range studied, with minimal accumulation following BID dosing. Available data, while not definitive, shows an absence of significant food effect.

**Distribution:** The apparent volume of distribution (V/D) of veliparib was large, and oral clearance was rapid.

**Metabolism:** Results from in vitro analysis reveal that this agent is metabolized by multiple isoenzymes – CYP1A1, 2D6, 2C19 and 3A4. Veliparib has one major metabolite in plasma, M8, a lactam derivative of the parent drug. The cellular PARP-inhibitory activity of M8 is 18-fold lower than veliparib.

**Excretion:** The average terminal half-life (t $\frac{1}{2}$ ) of veliparib ranged from 4 to 5 hours across dose levels. Recovery of the dose as parent drug in the urine over 24 hours after dosing averaged 78% (N = 6). Following multiple oral doses given twice daily, total recovery of the dose in the urine (as both parent drug and M8 metabolite) over 12 hours averaged 86% (N = 34). Veliparib is primarily cleared in the urine as intact parent drug along with metabolites, suggesting that renal function plays an important role in the clearance of veliparib and its metabolites.

**Patient Care Implications:** Patients may feel fatigue or tiredness. Loss of appetite and losing weight are common. Provide appropriate supportive care for diarrhea.

**How Supplied:** Veliparib (NSC 737664) will be provided free of charge by AbbVie Inc. and distributed by the Pharmaceutical Management Branch (PMB), Cancer Therapy Evaluation Program (CTEP), Division of Cancer Treatment and Diagnosis (DCTD), National Cancer Institute (NCI).

Veliparib 40 mg will be supplied as immediate release capsules in bottles containing 16 capsules or 64 capsules. The veliparib capsule contains veliparib, microcrystalline cellulose, colloidal silicon dioxide, magnesium stearate, gelatin, sodium lauryl sulfate, and titanium dioxide. May contain FD&C blue #1, FD&C yellow #6, or FD&C yellow #5.

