#### Veliparib Exposure

Pharmacokinetic (PK) sampling studies are proposed for all participating patients on the study V/T/C arm. Plasma trough levels will be obtained weekly through the first cycle to provide a steady-state assessment. Bone marrow or peripheral blood supernatant and blasts will be obtained pre-treatment and at C1D15. Only samples obtained on the V/T/C arm will be measured for veliparib using a validated liquid chromatography/tandem mass spectrometric (LC/MS/MS) method in the Analytical Pharmacology Core Laboratory at the Sidney Kimmel Comprehensive Cancer Center (SKCCC) at Johns Hopkins. Attempts to obtain dosing diary information and

PK sample times will be consistent across all patients. Steady-state plasma concentrations will be calculated for each patient. Exploratory correlative studies between veliparib exposure (plasma and bone marrow) with pharmacodynamic (biological endpoints, toxicity and efficacy) will be analyzed using nonparametric statistics. Significance for comparisons will be at the  $p < 0.05$  level.

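### Low creatinine clearance is expected to raise veliparib exposure and also lowers the chemotherapy dose in Arm A, and the exploratory exposure analyses in 13.5/13.6 make no allowance for it

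*Combined protocol and SAP*

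**What the plan says.** - **Entry (3.2.4).** The renal limit is "GFR greater than 30 ml/min per modified Cockcroft-Gault formula".
- **Chemotherapy (6.3).** For carboplatin: "CrCl 40-59 ml/min: 30% reduction (give 70% original dose"; at 16-39 ml/min, 55% of the dose is given. For topotecan: "CrCl 20-39 ml/min: 50% reduction", with no reduction above 40.
- **Veliparib (6.1, 6.2).** Section 6.2 reads "Veliparib dose will not be adjusted due to end organ dysfunction". The only route to a lower amount is in 6.1: "Patients unable to take veliparib due to toxicity will have those doses skipped".
- **Pharmacology (8.1.1).** "Recovery of the dose as parent drug in the urine over 24 hours after dosing averaged 78" (per cent, N = 6). The drug-interaction text says that "renal function plays an important role in the drug clearance and its metabolites" and asks for caution when carboplatin or topotecan is given with veliparib in pre-existing renal impairment.
- **Analysis (1.2, 13.5, 13.6).** Secondary objective 5 concerns veliparib exposure and its contribution to efficacy and toxicity. The plan for it is "Exploratory correlative studies between veliparib exposure (plasma and bone marrow) with pharmacodynamic" endpoints, by nonparametric statistics at p<0.05, using weekly cycle 1 plasma troughs and marrow samples from Arm A. Neither section names a covariate, stratum or sensitivity analysis for this work.

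**The concern.** Every Arm A patient starts on the same veliparib dose, so exposure differs between patients through clearance, and renal function is a main part of clearance. The same renal function fixes the chemotherapy tier. Patients with high veliparib exposure will tend to be those given less carboplatin and, below 40 ml/min, less topotecan.

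A direct correlation of exposure with response then mixes two effects. If reduced chemotherapy lowers response, the analysis can show less response at higher veliparib exposure when veliparib has no effect, or it can hide a real benefit. For toxicity the direction is harder to predict, because the chemotherapy cut and the higher veliparib exposure may act in opposite directions. Section 2.4 reports that phase I mucositis was dose limiting and correlated with veliparib exposure, so the toxicity half of objective 5 also needs an interpretable answer.

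**Working it through.** The documents give no power or effect size for objective 5, so there is no stated figure to reproduce. The check has three steps.

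**1. How exposure and dose move with CrCl.** The 78% urinary recovery and the 4-5 h half-life come from 8.1.1, the twice-daily dosing from 5.1, and the dose tiers from 6.3. Assumed: renal clearance proportional to CrCl, and a reference CrCl of 100 ml/min.

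Relative clearance r = 0.22 + 0.78 × CrCl/100, and AUC ratio = 1/r. At CrCl 50, r = 0.22 + 0.39 = 0.61, so the ratio is 1/0.61 = 1.64.

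The steady-state trough is proportional to e^(-12k)/(1 - e^(-12k)), with k = r × ln 2/half-life. At CrCl 50 and a 4 h half-life this is 0.391, against 0.143 at CrCl 100, a ratio of 2.74. With a 5 h half-life the ratio is 2.43.

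| CrCl | AUC ratio | Trough ratio | Carboplatin | Topotecan |
|---|---|---|---|---|
| 100 | 1.00 | 1.0 | 100% | 100% |
| 59 | 1.47 | 2.0-2.3 | 70% | 100% |
| 50 | 1.64 | 2.4-2.7 | 70% | 100% |
| 35 | 2.03 | 3.4-3.9 | 55% | 50% |
| 31 | 2.17 | 3.7-4.3 | 55% | 50% |

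With a reference of 90 to 120 ml/min, the AUC ratio from CrCl 59 to 31 spans about 1.4 to 2.4. Troughs, which the plan uses, respond more than AUC.

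**2. Bias in the estimate with no veliparib effect.** Assumed: CrCl normal, truncated to 30-150, with mean 100, 85 or 70 (5%, 15% or 30% of patients below 60); SD of log exposure at given CrCl 0.3 or 0.5. The log-odds of response are linear in the mean of the two relative doses, from 0.58 at full dose to 0.29 at the lowest tier, where the mean is (0.50 + 0.55)/2 = 0.525.

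| Share below 60 | Spearman, exposure with dose | Odds ratio per doubling, unadjusted | With delivered dose in the model |
|---|---|---|---|
| 5% | -0.19 to -0.28 | 0.94-0.97 | 1.00-1.01 |
| 15% | -0.27 to -0.40 | 0.85-0.94 | 0.99-1.01 |
| 30% | -0.31 to -0.46 | 0.79-0.90 | 1.01 |

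The true odds ratio is 1.00. In the 30% scenario, 41-47% of the high-exposure half had reduced chemotherapy, against 13-19% of the low-exposure half.

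**3. False-positive rate of a rank-sum test with 40 patients.** Assumed: two-sided 5% level (the plan does not state sidedness), CrCl SD 25 and log-exposure SD 0.3. Response by band (60 or more / 40-59 / below 40) is 0.58/0.35/0.14 for steep losses and 0.58/0.45/0.35 for milder ones.

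- 30% below 60, steep losses: about 12%. Milder losses: 7%. No loss from the cuts: 5%.
- 15% below 60: 6-8%.
- 5% below 60: about 5%.
- Stratified by CrCl, the test returns to about 5% in these scenarios.

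Under the model of step 2, the rate was 4-6% throughout. Its loss in the common 40-59 band is smaller: the mean dose is (1.00 + 0.70)/2 = 0.85, which gives a response probability of about 0.48.

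**The case against.** **The analysis is exploratory.** It covers at most 40 Arm A patients, and no decision or stopping rule depends on it. Nonparametric statistics is a class that could include a stratified rank test. This limits the consequence, but the text as written commits to no adjustment.

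**A lower dose need not mean lower exposure.** Renal reductions may only offset slower elimination of carboplatin and topotecan, in which case the bias through chemotherapy shrinks. This stands as a real uncertainty. Section 9 plans no topotecan or carboplatin levels, so the trial could not show it, and renal function would remain an unadjusted common cause.

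**The larger figures need assumptions that the documents do not supply.** This stands. No section gives the CrCl distribution or response in dose-reduced patients, and with few patients below 60 the problem is small.

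**Adjustment costs power.** This stands too. CrCl drives part of the exposure variation, and even with 30% below 60 only two or three Arm A patients would fall below 40.

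A reader might also infer stronger points that the documents do not support:

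- *The trial's main result is confounded.* The randomised CR/CRi comparison does not use veliparib exposure.
- *Section 6.2 is wrong, or the veliparib dose is excessive in renal impairment.* Section 8.1.1 asks for caution and does not require an adjustment. The exposure ratios rest on assumed linear scaling and a recovery figure from six patients, so they cannot settle a dosing question. Section 6.1 allows skipped doses, and 13.4 monitors toxicity by arm every 5 patients.
- *Section 3.2.4 contradicts itself by calling these patients normal.* It defines the term by the listed limits, so the wording is awkward but not in conflict.

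**Conclusion.** The point holds for objective 5. The protocol's own rules make CrCl a common cause of higher veliparib exposure and lower chemotherapy dose, and 13.5/13.6 allow for neither CrCl nor delivered dose. The firmer harm is a biased estimate: with no veliparib effect, the odds ratio per doubling of exposure falls to 0.94-0.97 if 5% of patients are below 60 ml/min and to 0.79-0.90 if 30% are. Inflated false positives are less certain, from about 5% to 12% depending on the scenario. A general doubling of the error rate should not be inferred, because it needs both many patients below 60 and steep response losses.

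These sizes rest on clearance proportional to CrCl, a 78% renal fraction, an assumed CrCl distribution and assumed response losses. The direction for response needs only that veliparib exposure rises as CrCl falls, as 8.1.1 implies, and that the reduced doses lower response.

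**What to change.** In 13.5 and 13.6, keep the unadjusted exposure-efficacy and exposure-toxicity results and add:

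1. A prespecified analysis accounting for baseline CrCl or delivered topotecan/carboplatin dose, for example a rank test stratified by CrCl below 60 versus 60 or more, or a partial rank correlation. Two strata are preferable to three, given how few patients are likely below 40.
2. A sensitivity analysis in patients given full-dose topotecan and carboplatin.
3. A statement that an association will not be attributed to veliparib unless it persists in the adjusted analysis.

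Creatinine is already in the study calendar, and the doses given should be on record, so the change is mainly analysis-plan wording. The cost is power. With 30% below 60 and a true odds ratio of 3 per doubling, power falls from about 40% to 30% with stratification if the dose cuts do not affect response. If they do, with steep losses, it rises from about 13% to 28%. Strata will be small, which is why the adjusted result should stand beside the unadjusted one.

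Separately, the sponsor should reconcile 6.2 with the renal-clearance and caution statements in 8.1.1. The topotecan bands in 6.3 (above 40, and 20-39) should also be reconciled, because they leave an eligible CrCl of exactly 40 unassigned. No dose or clinical rule is proposed here.

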### 6.3 Topotecan and Carboplatin Dose Reductions

Topotecan should dose-reduced for decreases in creatinine clearance (CrCl) using modified Cockcroft-Gault formula as follows:

CrCl >40 ml/min: no reduction

CrCl 20-39 ml/min: 50% reduction

CrCl <20 ml/min: topotecan will not be given

Carboplatin should be dose-reduced for decreases in CrCl as follows:

CrCl 40-59 ml/min: 30% reduction (give 70% original dose)

CrCl 16-39 ml/min: 45% reduction (give 55% original dose)

CrCl  $\leq$  15 ml/min: carboplatin will not be given.

## 7. ADVERSE EVENTS: LIST AND REPORTING REQUIREMENTS

### Rave-CTEP-AERS Integration

The Cancer Therapy Evaluation Program Adverse Event Reporting System (CTEP-AERS) integration enables evaluation of post-baseline AEs entered in Rave to determine whether they require expedited reporting, and facilitates entry in CTEP-AERS for those AEs requiring expedited reporting.

All AEs that occur after baseline are collected in Medidata Rave using the Adverse Event form, which is available for entry at each treatment or reporting period, and used to collect AEs that start during the period or persist from the previous reporting period. The Clinical Research Associate (CRA) will enter AEs that occur prior to the start of treatment on a baseline form that is not included in the Rave-CTEP-AERS integration. AEs that occur prior to enrollment must begin and end on the baseline Adverse Event form and should not be included on the standard Adverse Events form that is available at treatment unless there has been an increase in grade.

Prior to sending AEs through the rules evaluation process, site staff should verify the following on the Adverse Event form in Rave:

- The reporting period (course/cycle) is correct, and
- AEs are recorded and complete (no missing fields) and the form is query-free (fields added to the form during study build do not need to be query-free for the integration call with CTEP-AERS to be a success).

The CRA reports AEs in Rave at the time the Investigator learns of the event. If the CRA modifies an AE, it must be re-submitted for rules evaluation.

Upon completion of AE entry in Medidata Rave, the CRA submits the AE for rules evaluation by completing the Expedited Reporting Evaluation form. Both NCI and protocol-specific reporting rules evaluate the AEs submitted for expedited reporting. A report is initiated in CTEP-AERS using information entered in Medidata Rave for AEs that meet reporting requirements. The CRA completes the report by accessing CTEP-AERS via a direct link on the Medidata Rave Expedited Reporting Evaluation form.

In the rare occurrence that Internet connectivity is lost, a 24-hour notification is to be made to CTEP by telephone at [contact]. Once Internet connectivity is restored, the 24-hour notification that was phoned in must be entered immediately into CTEP-AERS using the deep link from Medidata Rave.

Additional information about the CTEP-AERS integration is available on the CTSU website:

- Study specific documents: Protocols > Documents > Education and Promotion, and
- Expedited Safety Reporting Rules Evaluation user guide: Resources > CTSU Operations Information > User Guides.

NCI requirements for SAE reporting are available on the CTEP website:

- NCI Guidelines for Investigators: Adverse Event Reporting Requirements is available at [https://ctep.cancer.gov/protocolDevelopment/electronic\\_applications/docs/aeguidelines.pdf](https://ctep.cancer.gov/protocolDevelopment/electronic_applications/docs/aeguidelines.pdf).

## 7.1 Comprehensive Adverse Events and Potential Risks List (CAEPR)

The Comprehensive Adverse Events and Potential Risks list (CAEPR) provides a single list of reported and/or potential adverse events (AE) associated with an agent using a uniform presentation of events by body system. In addition to the comprehensive list, a subset, the Specific Protocol Exceptions to Expedited Reporting (SPEER), appears in a separate column and is identified with bold and italicized text. This subset of AEs (SPEER) is a list of events that are protocol specific exceptions to expedited reporting to NCI (except as noted below). Refer to the 'CTEP, NCI Guidelines: Adverse Event Reporting Requirements' [http://ctep.cancer.gov/protocolDevelopment/electronic\\_applications/docs/aeguidelines.pdf](http://ctep.cancer.gov/protocolDevelopment/electronic_applications/docs/aeguidelines.pdf) for further clarification.

**NOTE:** Report AEs on the SPEER ONLY IF they exceed the grade noted in parentheses next to the AE in the SPEER. If this CAEPR is part of a combination protocol using multiple investigational agents and has an AE listed on different SPEERs, use the lower of the grades to determine if expedited reporting is required.

### 7.1.1 CAEPRs for CTEP IND Agent

#### 7.1.1.1 CAEPR for Veliparib

### Comprehensive Adverse Events and Potential Risks list (CAEPR) for ABT-888 (Veliparib, NSC 737664)

The Comprehensive Adverse Events and Potential Risks list (CAEPR) provides a single list of reported and/or potential adverse events (AE) associated with an agent using a uniform presentation of events by body system. In addition to the comprehensive list, a subset, the Specific Protocol Exceptions to Expedited Reporting (SPEER), appears in a separate column and is identified with bold and italicized text. This subset of AEs (SPEER) is a list of events that are protocol specific exceptions to expedited reporting to NCI (except as noted below). Refer to the 'CTEP, NCI Guidelines: Adverse Event Reporting Requirements' [http://ctep.cancer.gov/protocolDevelopment/electronic\\_applications/docs/aeguidelines.pdf](http://ctep.cancer.gov/protocolDevelopment/electronic_applications/docs/aeguidelines.pdf) for further clarification. Frequency is provided based on 2310 patients. Below is the CAEPR for ABT-888 (Veliparib).

**NOTE:** Report AEs on the SPEER **ONLY IF** they exceed the grade noted in parentheses next to the AE in the SPEER. If this CAEPR is part of a combination protocol using multiple investigational agents and has an AE listed on different SPEERs, use the lower of the grades to determine if expedited reporting is required.

Adverse Events with Possible Relationship to ABT-888 (Veliparib) (CTCAE 5.0 Term) [n= 2310]			Specific Protocol Exceptions to Expedited Reporting (SPEER)
Likely (>20%)	Less Likely (<=20%)	Rare but Serious (<3%)	
BLOOD AND LYMPHATIC SYSTEM DISORDERS			
	Anemia		Anemia (Gr 3)
	Febrile neutropenia		Febrile neutropenia (Gr 3)
GASTROINTESTINAL DISORDERS			
	Abdominal pain		
	Constipation		Constipation (Gr 2)
	Diarrhea		Diarrhea (Gr 3)
Nausea			Nausea (Gr 3)
	Vomiting		Vomiting (Gr 3)
GENERAL DISORDERS AND ADMINISTRATION SITE CONDITIONS			
Fatigue			Fatigue (Gr 3)
INVESTIGATIONS			
	Lymphocyte count decreased		Lymphocyte count decreased (Gr 4)
	Neutrophil count decreased		Neutrophil count decreased (Gr 4)
Platelet count decreased			Platelet count decreased (Gr 4)
	Weight loss		Weight loss (Gr 2)
	White blood cell decreased		White blood cell decreased (Gr 4)
METABOLISM AND NUTRITION DISORDERS			
	Anorexia		Anorexia (Gr 2)
	Dehydration		Dehydration (Gr 3)
	Hypophosphatemia		Hypophosphatemia (Gr 3)
NEOPLASMS BENIGN, MALIGNANT AND UNSPECIFIED (INCL CYSTS AND POLYPS)			
		Leukemia secondary to oncology chemotherapy	
		Myelodysplastic syndrome	
		Treatment related secondary malignancy	
NERVOUS SYSTEM DISORDERS			
	Dizziness		
	Dysgeusia		Dysgeusia (Gr 2)
	Headache		Headache (Gr 3)
		Seizure	
SKIN AND SUBCUTANEOUS TISSUE DISORDERS			
	Rash maculo-papular		
VASCULAR DISORDERS			
		Thromboembolic event 	

This table will be updated as the toxicity profile of the agent is revised. Updates will be distributed to all Principal Investigators at the time of revision. The current version can be obtained by contacting [[contact]](mailto:[contact]). Your name, the name of the investigator, the protocol and the agent should be included in the e-mail.

Thromboembolic events, including deep vein thrombosis and pulmonary embolism, have been observed at a higher frequency compared to control arm when administered in combination with temozolomide.

